6.4 COVARIATES

Not applicable.

7 HANDLING OF MISSING VALUES

In general, no imputation of missing data will be performed. Exceptions are described below. For categorical variables the number of missing values will be displayed in the respective tables. For at least interval-scaled variables the number of available observations will be displayed.

Incomplete dates will be handled as follows, if not specified otherwise:

If the day of a date is missing then the day is set to the 15th of the respective month. If day and month are missing then the date will be set to the middle of the respective year (in case of the year of the data cut: middle of time from beginning of year to data cut).

Missing values in PRO will be replaced according to the respective manual.

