For each patient, the safety event reporting period begins at the time of the patient's informed consent, which is obtained prior to the patient's enrollment in the study and lasts through the end of the observation period of the study; a report must be submitted to Pfizer Safety (or its designated representative) for any of the types of safety events listed in the table above occurring during this period. Most often, the date of informed consent is the same as the date of enrollment. In some situations, there may be a lag between the dates of informed consent and enrollment. In these instances, if a patient provides informed consent but is never enrolled in the study (eg, patient changes his/her mind about participation), the reporting period ends on the date of the decision to not enroll the patient. If the investigator becomes aware of a SAE occurring at any time after completion of the study and s/he considers the serious AE to be related to a Pfizer product, the SAE also must be reported to Pfizer Safety.

Causality assessment

The investigator is required to assess and record the causal relationship. For all AEs, sufficient information should be obtained by the investigator to determine the causality of each AE. For AEs with a causal relationship to abrocitinib, follow-up by the investigator is required until the event and/or its sequelae resolve or stabilize at a level acceptable to the investigator, and Pfizer concurs with that assessment.

An investigator's causality assessment is the determination of whether there exists a reasonable possibility that abrocitinib caused or contributed to an AE. If the investigator's final determination of causality is "unknown" and s/he cannot determine whether abrocitinib caused the event, the safety event must be reported within 24 hours.

If the investigator cannot determine the etiology of the event but s/he determines that abrocitinib did not cause the event, this should be clearly documented on the eCRF and in case of technical difficulties only, this also applies to the NIS AEM Report Form.

DEFINITIONS OF SAFETY EVENTS

Adverse events

An AE is any untoward medical occurrence in a patient administered a medicinal product. The event need not necessarily have a causal relationship with the product treatment or usage. Examples of AEs include but are not limited to:

• Abnormal test findings (see below for circumstances in which an abnormal test finding constitutes an AE);

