EASI	X	X	X	X	X	X

Study period based on routine visits	Baseline (Enroll ment)	Month 1	Month 3	Month 6	Month 9	Month 12 End of Study (EoS)
IGA	X	X	X	X	X	X
Pruritus-NRS	X	X	X	X	X	X
PP-NRS	X	X	X	X	X	X
DLQI	X	X	X	X	X	X
POEM	X	X	X	X	X	X
MOS	X	X	X	X	X	X
PBI	X	X	X	X	X	X
EQ-5D-5L	X	X	X	X	X	X
HADS	X	X	X	X	X	X

^{*} This includes patients who discontinued treatment with abrocitinib.

Figure 1. Timelines

The planned observation period of each patient is 12 months. In this time period up to 6 visits will be documented.

Figure 2. Study Period

Table 2. Definition of time windows for study visits

In order to collect comparable study data, Visits 1 to 3 occurring ± 14 days and Visits 4 to 6 occurring ± 28 days of the scheduled visit date will be used for data analysis (interim analysis).

Visit Label	Target Day	Definition [Day window]
Enrolment	1	1
Month 1	30	16 to 44
Month 3	91	77 to 105
Month 6	182	154 to 210
Month 9	273	245 to 301
Month 12	365	337 to 393

Visits that do not meet the defined windows as displayed in the table above will also be included in the final analysis and clinical study report. Therefore, all visits will be included using the visit time slots shown below. If more than one visit appears in a 3-month window, only the visit closest to the target day will be respected.

Amended definition:

Visit designation	Target Day	Definition [Day window]
Enrolment	1	1
Month 1	30	2 to 44
Month 3	91	45 to 105
Month 6	182	106 to 210
Month 9	273	211 to 301
Month 12	365	302 to 393

However, for analysis of safety parameters, all AEs/SAEs documented within the applicable reporting period will be analyzed.

- For the lab values, if the calculated study day for the labelled baseline visit is not study Day 1, but falls within 40 days before the start of the study dosing, then that data should be used for the baseline instead of leaving baseline missing.
- For the other values, if the calculated study day for the labelled baseline visit is not study Day 1, but falls before the start of the study dosing, then that data should be used for the baseline instead of leaving baseline missing.
- If baseline is missing there will be no imputation and although the subject's data will be included in summary data it will not be included in any change from baseline analyses.

If two or more routine visits fall into the same window, keep the one closest to the Target Day. If two routine visits are equal distance from the Target Day in absolute value, the later visit should be used.

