8.2.1 Safety Analyses

Treatment-emergent adverse events are adverse events which worsen or start after start of treatment with abrocitinib but no later than 28 days after end of treatment with abrocitinib.

In addition to the analysis of treatment-emergent adverse events and drug-related adverse events as specified in 6.2 adverse events which occurred under another systemic treatment, following cessation of abrocitinib, will be given and presented in a separated listing. Number and percentage of SOC and PT will be presented according to maximal grade.

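### The default for partial dates (15th of the month, mid-year) can remove an adverse event's treatment-emergent label at either end of the treatment window

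*SAP*

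**What the plan says.** SAP section 7 opens its date rule with "Incomplete dates will be handled as follows, if not specified otherwise". Two defaults follow. The first is "If the day of a date is missing then the day is set to the 15th of the respective month". The second is "If day and month are missing then the date will be set to the middle of the respective year"; in the year of the data cut, the midpoint between 1 January and the cut is used instead.

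SAP 8.2.1 then classifies events by date: "Treatment-emergent adverse events are adverse events which worsen or start after start of treatment with abrocitinib but no later than 28 days" after the end of abrocitinib. It links this class to the safety tables with the words "In addition to the analysis of treatment-emergent adverse events and drug-related adverse events as specified in 6.2".

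Two other statements bear on the point. SAP 1.1 (and protocol 9.7) says that "for analysis of safety parameters, all AEs/SAEs documented within the applicable reporting period will be analyzed". Protocol section 11 says that "the safety event reporting period begins at the time of the patient's informed consent", so events from before the first dose can be in the database.

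SAP 6.3 and Appendix 1 compute treatment duration as last date minus first date plus one. No separate rule for partial adverse event onset dates or partial treatment dates appears in SAP 6.2, 6.3, 8.2.1, Appendix 1 or the protocol.

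**The concern.** The default ignores the date of first dose. If treatment began after the 15th and an event is recorded only by that month, the event is dated to the 15th, which precedes treatment. It then fails the condition "adverse events which worsen or start after start of treatment with abrocitinib" even if it began on drug. The same happens on a yearly scale when only the year is known and treatment began after mid-year. At the other end, an event within 28 days of stopping can be pushed past the limit.

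At stake is the treatment-emergent summary, and within it the events soon after drug start and soon after drug stop. A partial stop date can also be placed before the start date, which corrupts the duration summary and the window that depends on it.

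**Working it through.** **No figure to reproduce.** The plan gives no rate of partial dates and no estimate of their effect. The check is an enumeration of calendar dates under the SAP 7 rule.

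**Inputs from the documents:** the 15th; mid-year (1 July used here); onset after first dose; the limit of 28 days after last dose; 12 months of observation.

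**Assumptions:** first dose uniform over the 365 days of 2023; true onset uniform from the day after first dose to 28 days after last dose; continuous exposure of T = 28, 91 or 365 days.

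**Single cases**

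- First dose 20 March, true onset 25 March, day missing: dated 15 March, before first dose.
- First dose 4 October, true onset 10 November, day and month missing: dated 1 July, before first dose.
- Last dose 10 March, so the window ends 7 April. True onset 3 April, day missing: dated 15 April, outside the window.
- Opposite direction: first dose 10 March, true onset 5 March (after consent), day missing. It is dated 15 March and becomes treatment-emergent.
- Duration: start 20 March, stop recorded as March only: 15 − 20 + 1 = −4 days.

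**Day missing, onset in the month of first dose**

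- 30-day month, onset on or after dose day: pairs with dose day after the 15th are 15 + 14 + … + 1 = 120, of 465 in all. 120/465 = 25.8%.
- Onset strictly after dose day: 14 + 13 + … + 0 = 105, of 435. 105/435 = 24.1%.
- Actual 2023 calendar, strictly after: 1,338/5,373 = 24.9%. If an imputed date equal to the first-dose date also fails *after*, the share is 28.3%.
- The 15th precedes first dose for 185 of 365 possible first-dose dates (50.7%).

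**Day and month missing, onset in the year of first dose:** 16,653/66,430 = 25.1%. 1 July precedes first dose for 183 of 365 dates (50.1%).

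**Whole treatment-emergent window.** The window has T − 1 + 28 = T + 27 possible onset days for each first-dose date. With the day missing, only events in the first-dose month can be dated before first dose, so the share is 1,338/(365 × (T + 27)):

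- T = 28: 1,338/20,075 = 6.7%
- T = 91: 1,338/43,070 = 3.1%
- T = 365: 1,338/143,080 = 0.9%

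All enumerated shares of truly emergent events with an incomplete onset date:

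| Exposure | Day missing: before first dose | Day missing: past 28-day limit | Day and month missing: before first dose | Day and month missing: past 28-day limit |
|---|---|---|---|---|
| 28 days | 6.7% | 6.3% | 42.5% | 42.2% |
| 91 days | 3.1% | 2.9% | 33.8% | 33.6% |
| 365 days | 0.9% | 0.9% | 11.6% | 11.6% |

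The two ends are mutually exclusive, so the shares within a row add. For 28 days and a missing day, 6.67 + 6.28 = about 13.0%. In the 365-day row the window runs past the 12-month observation, so its upper-end figures matter little in practice. Cutting that window at 364 onset days changes the lower-end figure only to 1,338/(365 × 364) = 1.0%.

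Every percentage here is a share of events with incomplete dates, not of all adverse events.

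**The case against.** The case against giving this weight has several parts.

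- **Events stay in the data.** SAP 1.1 and protocol 9.7 require all events in the reporting period to be analysed, and SAP 6.2 defines its endpoint over all adverse events. A reader might infer that events vanish from the report. The documents do not support that: the event loses a label. Still, SAP 8.2.1 describes the SAP 6.2 analysis as one of treatment-emergent and drug-related events, and SAP 6.2 lists no separate all-event table beside it. The label therefore matters.
- **A rule may exist elsewhere.** The SAP 7 default yields to any other specification, SAP 6.2 refers to sponsor data standards, and SAP 9 refers to separate table shells. None of these is reproduced. This limit stands.
- **Partial dates may be rare.** Events are collected prospectively over 12 months, with automated queries and manual completeness checks (protocol 9.6). An event with both day and month unknown should be unusual. This also stands, and the actual count is unknown.
- **The effect is not one-sided.** A reader might infer that the rule can only lower treatment-emergent counts. It can also move pre-dose events in, because reporting starts at consent. The schedule marks adverse events only from Visit 2, so that stock is probably small, but this is a judgement rather than a documented fact.
- **The quarter is a worst subset.** A reader might take 24–26% as a share of adverse events. It applies only to day-missing events in the first-dose month.
- **The study is descriptive.** There are no hypotheses or decision rules, safety is an explorative objective, and serious events are reported within 24 hours whatever the SAP says. This lowers the stakes but does not make the classification correct.

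**Conclusion.** The point holds as a defect of classification. As written, the SAP 7 default can date an on-treatment event before first dose or beyond the 28-day limit, and SAP 8.2.1 then withholds the treatment-emergent label.

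The effect is concentrated. It is appreciable for events early in treatment, for short exposures and for dates known only by year. It is about 1% at the first-dose end for day-missing events when exposure lasts 12 months. These sizes rest on uniform dosing and onset dates and on continuous exposure. The absolute number of events affected cannot be stated, because the number of partial dates is not given. The negative duration follows directly from the stated formula and needs no distributional assumption.

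The conclusion would fall away if the sponsor data standards or table shells already contain a rule covering both ends of the window. SAP 7 should then cite it.

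**What to change.** Three edits to the SAP before database lock:

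1. **SAP 7, adverse event onset.** If the known part of the onset date is compatible with onset between first dose and 28 days after last dose, set onset to the later of the first-dose date and the first day of the known month or year, unless the event's end date is before first dose. Count the event as treatment-emergent.
2. **SAP 7, treatment stop.** Impute a partial stop date no earlier than the start date and no later than the end of observation. Apply this before the onset rule, which depends on the last-dose date.
3. **SAP 8.2.1.** Replace *after* start of treatment with *on or after*. Otherwise an onset set to the first-dose date might still fail the definition.

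In the enumeration, setting onset no earlier than first dose whenever the partial date allows it reduces the share of truly emergent events dated before first dose to 0% in every scenario. At the other end, the case with last dose on 10 March and onset in April is dated 1 April, inside the window ending 7 April.

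The cost is a few sentences and some programming, with no new data. The price is a deliberate lean towards inclusion. Treatment-emergent counts may rise slightly and will include a few events that truly began before first dose or after the window.

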8 STATISTICAL METHODOLOGY AND STATISTICAL ANALYSES

8.1 STATISTICAL METHODS

All parameters will be evaluated in a descriptive respective explorative manner. Binary, categorical and ordinal parameters will be summarized by means of absolute and percentage numbers within the various groups (including 'missing data' as valid category). Those variables will be compared for the subgroups in an explorative manner using Chi-Square test respective Fisher's exact test if a sample size of at least 30 in each subgroup is not reached. Numerical data will be summarized by means of standard statistics (i.e. number of available data, number of missing data, mean, standard deviation, minimum, median and maximum) and compared exploratively for the subgroups by Mann-Whitney-U-test. Due to the descriptive/explorative manner of the analysis no adjustment for multiple testing will take place. Graphical displays may be used.

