
1.2 STUDY POPULATION

In total, this non-interventional study aims to enroll at least 750 patients patients at approximately 80 study sites across Germany. The planned enrollment period is 48 months. With a planned observation duration of 12 months per patient, the entire study would last for 60 months. The non-interventional study started in April 2022 and will end in May 2027.

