5.4 SUBGROUPS

The following subgroups will be analysed:

- Sequence of dosage (50 mg → 100 mg vs. 100 mg → 50 mg vs. 100 mg → 200 mg vs. 200 mg → 100 mg vs. 200 mg vs. 50 mg)
- Medication history* (prior conventional systemic treatment, prior biologic, prior JAKi, none of those)
- Dosage switchers (patients who switched from abrocitinib vs. patients who remain on abrocitinib)
- Abrocitinib responder, defined as: EASI-75-responder and/or SCORAD-75-responder and/or IGA 0/1
- EASI-90 responder (yes vs. no)

If less than 20 patients are in one subgroup class, classes will be combined in a meaningful way or the subgroup analysis will be omitted with reason.

*Pfizer will assign the prior medication documented to (i) topical (TCS,TCI,other), (ii) systemic (conventional, biologics, JAKi, other), (iii) phototherapy and (iv) other in order to analyze the pretreatment and form the subgroup "medication history" accordingly.

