Smoking history and current smoking status	Baseline characteristics, potential confounder	Case records	Frequency analysis
Renal and/or liver impairment	Baseline characteristics	Case records	Frequency analysis
Comorbidities at baseline	Baseline characteristics, potential confounder, potential subgroup identifier	Case records	Frequency analysis
If positive anamnesis at baseline exists: Improvement of (allergic) asthma symptoms from baseline	Baseline characteristics, potential confounder, potential subgroup identifier	Case records	Frequency analysis
If positive anamnesis at baseline exists: Improvement of (allergic) rhinitis symptoms from baseline	Baseline characteristics, potential confounder, potential subgroup identifier	Case records	Frequency analysis
If positive anamnesis at baseline exists: Improvement of polyposis nasi symptoms from baseline	Baseline characteristics, potential confounder, potential subgroup identifier	Case records	Frequency analysis
If positive anamnesis at baseline exists: Improvement of alopecia areata from baseline Baseline characteristics, potential confounder, potential subgroup identifier		Case records	Frequency analysis

If positive anamnesis at baseline exists: Improvement of chronic hand eczema symptoms from baseline	Baseline characteristics, potential confounder, potential subgroup identifier	Case records	Frequency analysis
If positive anamnesis at baseline exists: Improvement of prurigo nodularis symptoms from baseline	Baseline characteristics, potential confounder, potential subgroup identifier	Case records	Frequency analysis
Previous treatments for diagnosed AD	Baseline characteristics, potential confounder, potential subgroup identifier	Case records	Frequency analysis
Concomitant treatment of AD (and dosage)	Baseline characteristics, Exposure, explorative outcome, potential confounder, potential subgroup identifier	Case records	Frequency analysis and Summary statistics (n, mean, median, standard deviation, minimum and maximum) for dose
Concomitant (non-AD) treatment	Baseline characteristics, outcome, potential confounder, potential subgroup identifier	Case records	Frequency analysis with respect to level 1 and level 2 of ATC codes
Dosage of abrocitinib used	Exposure, potential confounder, explorative outcome variable, potential subgroup identifier	Case records	Summary statistics (n, mean, median, standard deviation, minimum and maximum)

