Outcome **Analysis Set Supports Missing Data** Subgroups Statistical Method Covariates/ Strata Protocol **Objective** Number baseline)/score at baseline*100 Mann-Whitney-U test for subgroups Change of EuroQol five-(score at respective FAS, mFAS, PP All None Excluded dimensional-five level visit - score at (EQ-5D-5L) from baseline)/score at 21 baseline baseline*100 Mann-Whitney-U test for subgroups Change of PBI from FAS, mFAS, PP All (score at respective None Excluded visit - score at baseline baseline)/score at 22 baseline*100 Mann-Whitney-U test for subgroups Patient's satisfaction FAS, mFAS, PP All Frequency tables for None Excluded satisfaction with with treatment (PBI after baseline) effectiveness and tolerability 23 Chi-Square test respective Fisher's exact test for subgroups Number of days with FAS, mFAS, PP All Excluded Summary statistics (n, None topical-treatment use mean, median, standard deviation, (TCS, TCI) 24 minimum and maximum) Mann-Whitney-U test for subgroups Number of days with FAS, mFAS, PP All Summary statistics (n, None Excluded emollients use mean, median, standard deviation, 25 minimum and maximum)

Outcome	Analysis Set	Supports Protocol Objective Number	Subgroups	Statistical Method	Covariates/ Strata	Missing Data
				Mann-Whitney-U test for subgroups		
AD-treatment with abrocitinib and/or without topicals – total days	FAS, mFAS, PP	26	All	Summary statistics (n, mean, median, standard deviation, minimum and maximum) Mann-Whitney-U test for subgroups	None	Excluded
AD-treatment with abrocitinib and/or without topicals – stratified by abrocitinib dose	FAS, mFAS, PP	27	All	Summary statistics (n, mean, median, standard deviation, minimum and maximum) Mann-Whitney-U test for subgroups	None	Excluded
Number of flares	FAS, mFAS, PP	28	All	Summary statistics (n, mean, median, standard deviation, minimum and maximum) Mann-Whitney-U test for subgroups	None	Excluded

All explorative endpoints mentioned in section 6.3 will be analyzed for FAS and all subgroups, respectively. Safety enpoints, as given in section 6.2 will be analyzed for SAF.

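### SAP 8.1 picks chi-square or Fisher's exact test by a subgroup size of 30 rather than by expected cell counts, which distorts exploratory p-values in very sparse tables and in comparisons with small classes

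*SAP*

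**What the plan says.** SAP 8.1 has binary, categorical and ordinal parameters compared between subgroups by chi-square on an exploratory basis, with Fisher's exact test taking over "if a sample size of at least 30 in each subgroup is not reached". The 8.2.3 summary table repeats the pair of tests without a criterion, and Appendix 2, which could have held further detail, is marked not applicable. Expected cell counts are not mentioned anywhere, nor is a continuity correction or a nominal level.

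Three other provisions decide which tables the rule meets:

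- SAP 5.4: "If less than 20 patients are in one subgroup class, classes will be combined in a meaningful way", or the analysis is dropped. The Fisher branch therefore covers tables whose smallest class has 20-29 patients.
- SAP 5.4 also defines subgroups with several classes, for example medication history in four ("prior conventional systemic treatment, prior biologic, prior JAKi, none of those") and a multi-class dosage sequence. No class sizes are given. SAP 1.2 says "this non-interventional study aims to enroll at least 750 patients".
- SAP 8.2.3 ends with: "All explorative endpoints mentioned in section 6.3 will be analyzed for FAS and all subgroups, respectively". Section 6.3 includes renal or liver impairment, baseline comorbidities and non-AD medication ("Frequency analysis with respect to level 1 and level 2 of ATC codes").

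**The concern.** Pearson's statistic follows its reference distribution only if the expected counts are not too small. A class of 30 says nothing about that. With a 1% characteristic its expected count is 30 x 0.01 = 0.3, and the SAP still prescribes chi-square. Conversely, a class of 20 with a 30% response has an expected count of 20 x 0.30 = 6, for which chi-square is adequate, yet the SAP prescribes Fisher.

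SAP section 4 makes these subgroup tests the means of generating hypotheses, and SAP 8.1 plans no multiplicity adjustment. Unadjusted p-values will therefore draw attention to some differences and not to others. A rule keyed to the wrong quantity tends to flag rare characteristics too often and common responses in small classes too seldom.

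**Working it through.** **Inputs.** From the documents: the switch at 30, the floor of 20 per class, and a total of at least 750. Assumed, because the documents give none: two-sided 5%, the class sizes, the event rates, and Pearson chi-square without correction. The plan has no figure of its own to reproduce.

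**Formulas.** For a 2x2 table with x of n1 and y of n2, m = x + y and N = n1 + n2:

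- smallest expected event count = min(n1, n2) x m / N
- X² = N [x(n2 - y) - y(n1 - x)]² / [n1 n2 m (N - m)], rejected at 3.84 or more
- size = sum of the binomial probabilities of all rejected tables at a common rate

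Sizes for two classes are exact enumerations; those for more classes are simulated.

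**One case by hand: 30 v 300 at 0.5%.**

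- x=1, y=0: X² = 330 x 300² / (30 x 300 x 1 x 329) = 10.0, rejected.
- x=1, y=1: X² = 330 x 270² / (30 x 300 x 2 x 328) = 4.08, rejected.
- x=1, y=2: X² = 330 x 240² / (30 x 300 x 3 x 327) = 2.15, not rejected.
- P(x=1) = 30 x 0.005 x 0.995^29 = 0.130. P(y≤1) = 0.995^300 + 300 x 0.005 x 0.995^299 = 0.557. The product is 0.072.
- P(x≥2) = 0.0099, nearly all of it rejected, which brings the size to 0.082.

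So a single event in the small class usually suffices for nominal significance.

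**Chi-square branch (every class at least 30), size of Pearson chi-square:**

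| Classes | 0.5% | 1% | 2% | 5% |
|---|---|---|---|---|
| 30 v 300 | 8.2% | 7.4% | 5.2% | 4.0% |
| 30 v 720 | 7.7% | 5.1% | 5.3% | 4.2% |
| 100 v 650 | 5.2% | 4.6% | 4.0% | 4.7% |
| 30/30/30/660 | 9.1% | 8.1% | about 6.5% | 5.4% |
| 5 x 30 + 600 | 14.4% | 10.0% | 7.4% | 5.8% |

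Several rare categories in one variable make it worse: with four 1% categories, 30 v 720 gives 8.7%. With equal classes of 30 and rates up to 5%, the size is below nominal.

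**A single table.** For 1/30 v 3/720 the smallest expected count is 30 x 4 / 750 = 0.16. X² = 750 x 630² / (30 x 720 x 4 x 746) = 4.62, so p = 0.032. Fisher's p is 0.151. The rule alone decides whether this difference is flagged.

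**Fisher branch (smallest class 20-29), common outcomes:**

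| Classes | Response | Fisher size | Pearson size |
|---|---|---|---|
| 29 v 29 | 30% | 2.5% | 4.7% |
| 29 v 29 | 50% | 2.5% | 4.8% |
| 29 v 721 | 30% | 3.8% | 4.9% |
| 29 v 721 | 50% | 3.6% | 5.0% |

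Power, Pearson against Fisher: 0.86 v 0.78 for 25 v 25 (30% v 70%), and 0.86 v 0.83 for 25 v 725 (30% v 60%). The loss is material when the compared classes are equal and small, and a few points when one small class faces the rest of the cohort.

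**The case against.** The strongest reply has four parts.

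- **No error rate is being controlled.** SAP 8.2 calls the subgroup tests purely exploratory, SAP 4.1 and 4.2 declare hypotheses and decision rules not applicable, and no level is stated. This stands as a limit on importance. It does not justify choosing a test by an irrelevant criterion when a correct one costs nothing.
- **The rare variables may not be tested at all.** A reader might infer that every categorical variable in 6.3 is tested in every subgroup. The documents do not settle this. SAP 8.1 is general and 8.2.3 has the 6.3 endpoints analysed for all subgroups, but section 4 limits the tests to those mentioned in 8.2.3. There, chi-square or Fisher is attached only to the IGA, EASI, pruritus, DLQI and PBI outcomes, and the 6.3 definitions for categorical variables say only frequency analysis. On the narrow reading the anti-conservative half largely falls away.
- **The improvement variables are weak examples.** Those for polyposis nasi or alopecia areata are restricted to patients affected at baseline. If the 30 refers to evaluable patients, Fisher may already apply; if it refers to class size, chi-square does. The SAP does not say which.
- **The inflation depends on the scenario.** At the planned 750, 30 v 720 at 1% is 5.1%. With a Yates correction, 30 v 300 gives 0.8% and 1.7% at 0.5% and 1%. Both limits stand.

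**Conclusion.** The criterion is wrong in kind, and the consequence is small and confined. Under the stated assumptions, chi-square is noticeably anti-conservative only at rates of about 1-2% or less, with a class near 30 facing a much larger one or with many classes. The size is then roughly 7-9% for two to four classes and up to 14% in the most extreme six-class layout. Two-class tables such as 100 v 650 are close to nominal. The opposite error, Fisher's conservatism with common outcomes, is clear for two small equal classes and modest for one small class against the rest.

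The first error matters for sparse baseline variables such as organ impairment, comorbidities and ATC groups, to the extent that SAP 8.1 and 8.2.3 mean them to be tested. A reader might infer that the study's error rates are unsound in general or that the primary results are affected. The documents do not support either: the primary analysis is descriptive, its response proportions do not depend on this rule, and the effect on the primary-endpoint subgroup tests is small unless the compared classes are all small. This is a minor methods correction.

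**What to change.** In SAP 8.1, replace the clause on a sample size of 30 with: Pearson chi-square without continuity correction when all expected cell counts are at least 5; otherwise Fisher's exact test with mid-p for 2x2 tables, or a Monte Carlo exact test for larger tables.

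Mid-p is preferable to ordinary Fisher because the latter over-corrects. For 30 v 300 at 0.5% and 1%, ordinary Fisher has size 0.8% and 1.7%, and mid-p 3.8% and 3.6%. In the unequal two-class layouts above (30 v 300, 30 v 720, 100 v 650, 29 v 721), the proposed rule has size 2.5% to 5.2% at rates from 0.5% to 50%.

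The cost is one sentence and standard software options, with no change to data, endpoints or analysis sets. There are two small downsides: mid-p does not strictly guarantee the nominal level, and sparse tables will be flagged less often than under the present rule.
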